### **3.7. Assessment of changes in outcomes (at a service level)**

Aggregate programme level data will be obtained from the two services for a three - six month period in 2024 when trained staff have delivered programmes and a corresponding three- six month period in 2023. This will allow comparable measurement of change over time at a service level.

For the weight management service, a control group will consist of programmes run by non-trained staff. The same aggregated data will be obtained for this control group. Individual level patient data will not be shared with researchers because not all service users will have consented to this.

The aggregate data will include:

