## DCHS NHS Pulmonary Rehabilitation Programme

We would expect the increase in the mean CRDQ score at 6 weeks in 2024 (post training) to be larger than the increase in the mean CRDQ score in 2023 (pre training). We are unlikely to have statistical power to detect small differences based on numbers of service users if we limit the 'post' time period to the three month study period in 2024 and the corresponding 'pre' time period in 2023. We need to extend this request for data to cover a six month period.

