## **6.Timescales**

(Ethics outcome dependent)-

June- July 2024 - Recruitment of staff participants and pre intervention staff observations.

July- August 2024 - Delivery of training package and pre and immediately post intervention staff questionnaires.

July – November 2024 – Recruitment of service users and baseline outcome measures and Health Literacy Questionnaire data collection.

August– February 2025 – Service user post intervention outcome measures and Health Literacy Questionnaire data collection.

September – October 2024 – Two month follow up staff questionnaires.

October – November 2024 – Post intervention staff observations and/or recording of consultations.

November - January 2025 – Staff focus group interviews.

August 2024– March 2025 - Data analysis.

January – March 2025 – Write report/disseminate.

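### Pulmonary rehabilitation: the six-month service-level window said to be needed does not fit the 2024 schedule, and the analysis section still uses three months

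*Combined protocol and SAP*

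**What the plan says.** - **Section 3.9.3 (pulmonary rehabilitation).** The expectation is stated as "We would expect the increase in the mean CRDQ score at 6 weeks in 2024 (post training) to be larger" than the 2023 increase. The text then says that three months in each year is unlikely to give power for small differences, and concludes: "We need to extend this request for data to cover a six month period".
- **Section 3.7.** Aggregate data are requested for a "three - six month period in 2024 when trained staff have delivered programmes" and "a corresponding three- six month period in 2023".
- **Section 3.5 (outcome timing).** The service takes all its measures, including the CRDQ, at 0 and 6 weeks.
- **Section 3.2.** All six physiotherapists and both specialist nurses are trained, so this service has no concurrent untrained group.
- **Section 6.** Training is listed as "July- August 2024 - Delivery of training package and pre and immediately post intervention staff questionnaires". June to July is given to "Recruitment of staff participants and pre intervention staff observations". Service-user outcome collection runs to February 2025, and analysis and reporting run to March 2025. The timetable is marked as depending on the ethics outcome. It gives no date for the aggregate extract.
- **Section 3.10.5.** The aggregate analysis compares three months before training with three months after it.

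**The concern.** The longer window is the plan's only stated answer to low power in the pulmonary rehabilitation before-after comparison. That comparison is also this service's only service-level contrast on its primary outcome. If six post-training months are not available where the plan places them, the data request will be met in one of two ways. The service may supply a six-month block that includes delivery before all eight staff were trained, which dilutes the contrast. Or it may supply roughly three months, which section 3.9.3 regards as too little for small differences. Section 3.10.5 points to the second outcome, because its window was never lengthened.

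**Working it through.** **The plan's own figure.** Section 3.9.2 gives 96 to 144 joiners in three months. Two cohorts × 6 venues × 8 = 96, and × 12 = 144, so this reproduces. No CRDQ sample size, SD or target difference is given, so there is no power figure to reproduce.

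**Inputs.** Training completes between 1 July and 31 August 2024 (section 6). Follow-up is 42 days (section 3.5). The window is six months (section 3.9.3). One month is taken as 30.4375 days.

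**Step 1: starters with a six-week outcome in 2024.** The last eligible start is 31 December − 42 days = 19 November 2024.
- All staff trained by 1 July: 1 July to 19 November = 31 + 31 + 30 + 31 + 19 = 142 days = 4.7 months.
- Training complete on 31 August: 1 September to 19 November = 30 + 31 + 19 = 80 days = 2.6 months.

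Six months (183 days) of such starters would need training complete by about 19 November − 183 days = 20 May 2024. With an end-August finish, even the three-month lower end in section 3.7 is missed.

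**Step 2: counting by delivery date.** July to December 2024 is 184 days, or six months. It is wholly post-training only if all eight staff finish by 1 July. If they finish on 31 August, 31 + 31 = 62 days come before completion: 62/184 = 34%.

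**Step 3: letting the window run into 2025.**
- Outcomes to 28 February 2025: the last start is 17 January 2025. That gives 201 days of starters from 1 July, or 139 from 1 September. Six months is reached only if training ends by about 17 January − 183 days = 18 July 2024.
- Outcomes to 31 March 2025: the last start is 17 February 2025. That gives 170 days (5.6 months) from 1 September, with no time left for analysis.
- Full six months after an end-August finish: starts run to about 2 March 2025, and the last outcomes fall at about 2 March + 42 days = 13 April 2025.

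**Step 4: what this means for precision (illustration).** Assumptions: independent service users, equal numbers in 2023, complete outcomes, 80% power, two-sided 5%, and 96/3 to 144/3 = 32 to 48 joiners a month. Detectable difference in SD units = 2.80 × √(2/n), with n per period.

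| Window | n per period | Detectable difference (SD) |
|---|---|---|
| 2.6 months | 83 to 125 | 0.43 to 0.35 |
| 3 months | 96 to 144 | 0.40 to 0.33 |
| 4.7 months | 150 to 226 | 0.32 to 0.26 |
| 6 months | 192 to 288 | 0.29 to 0.23 |

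For example, 2.80 × √(2/83) = 0.43 and 2.80 × √(2/288) = 0.23.

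**The case against.** The strongest reply is that section 3.7 defines the window by when trained staff deliver, and does not require both start and outcome to fall in 2024. It also allows three to six months. The sentence asking for six months names no year, so an extension into 2025 is compatible with it.

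This has force. A reader might infer that a six-month post-training block is impossible, and the documents do not support that. By delivery date, six months fit if everyone is trained by 1 July. By start date, they fit with outcomes to end February 2025 if training ends by about 18 July. No section says when the eight pulmonary rehabilitation staff finish. The July-August slot covers the whole training package, so 31 August is the latest case and not a stated date.

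A reader might also take February 2025 as a hard stop. That line concerns outcome measures and questionnaires from service users, not the summaries supplied by the services. Only the March 2025 end of analysis and reporting clearly limits the aggregate data.

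The loss is also modest at the favourable end: 0.26 to 0.32 SD at 4.7 months against 0.23 to 0.29 SD at six.

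What remains is this. Section 3.9.3 does refer to the six-week CRDQ in 2024, and no section extends the aggregate window into 2025. Completion by 1 July sits badly with pre-training observations scheduled into July and training into August. The dates are provisional, but a delay makes the fit worse. The conflict between section 3.9.3 (six months) and section 3.10.5 (three) needs no calendar assumption at all.

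**Conclusion.** The point holds as a conflict between the stated data need, the schedule and the analysis section. On the current timetable, with outcomes counted in 2024, the post-training window is 2.6 to 4.7 months and not six. The delivery-date reading reaches six months, but up to 34% of that block comes before training is complete. If the window runs into 2025, feasibility turns on the training completion date: about 18 July for outcomes by end February, while an end-August finish takes the last outcomes past March 2025.

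The day counts rest only on the section 6 dates and the six-week follow-up. The SD figures rest on the assumptions listed with them. With no CRDQ SD or target difference in the plan, it cannot be said that six months would be enough, or that a shorter window would fail against a defined target. The point should be settled before the data request goes out. It does not bear on the weight management calculation.

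**What to change.** In sections 3.7, 3.9.3 and 3.10.5, define the pulmonary rehabilitation post period in the same words: people starting in the 26 weeks after the last of the eight staff is trained, compared with people starting in the same calendar weeks one year earlier. On the current timetable that comparison period is still wholly before training. Add to section 6 a date for the aggregate extract, set at the last start plus six weeks. This is about mid-April 2025 at the latest on present dates, and later if ethics approval moves training.

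If March 2025 is fixed, replace the six-month figure in section 3.9.3 with the window that the calendar allows, state the detectable difference that it gives and the assumptions behind it, and make sections 3.7 and 3.10.5 match.

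The cost is about six weeks' delay to one aggregate table under the first option, or a less favourable stated precision under the second. Neither needs extra recruitment.

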### **3.10 Data analysis**

The study will produce both qualitative data and quantitative data. The analysis of the different types and sets of data will occur separately.

#### 3.10.1 Qualitative data

The qualitative data will be analysed based upon Framework analysis (Ritchie & Lewis, 2003). Analysis will follow the four stages of this approach: familiarisation, identification of a thematic framework, charting, and then mapping and theorising. A spreadsheet or code book will be used to organise and compare and contrast the data (Richie & Lewis 2003). NVIVO 12, an electronic qualitative data management tool, will be used to store and organise the data.

#### 3.10.2 Observations

There will be 24 completed checklists for 12 members of staff observed before and after the training. For each health literacy technique, a 2x2 table will be created. This is so we can compare the % of Verbal Health Literacy technique used, most/all of the time versus sometimes/never, pre training and post training. We will make this comparison using McNemar's Test.

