### **3.4. Assessment of change in how staff use Verbal Health Literacy techniques in practice**

To assess if there is a change in the frequency with which staff use the techniques they have learnt in practice, the lead researcher will observe or record programme sessions before and 12-16 weeks after staff have been trained. The lead researcher will observe the extent to which the Health Literacy techniques 'simple language', 'teach-back' and 'chunk and check' are used. The researcher will attend in person or ask the staff member to record programme sessions on an encrypted recorder. The researcher will use a checklist to describe how often each of the three communication techniques are used: never, sometimes, most of the time, all of the time. All staff from the two services, who will be receiving the training, will be approached for permission to assess two of their sessions (4 staff in the weight loss service and 8 staff in the pulmonary rehabilitation service). If all agree the researcher will observe 24 sessions in total. That is, twelve before they receive the training and twelve after.

Consent will be gained from all staff prior to collecting their data. The focus of this part of the project is on staff behaviour. Service users will be involved incidentally. Even so, verbal consent will also be gained from service users prior to the researcher observing programme sessions.

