### **3.9 Sampling strategy and sample size**

#### **3.9.1. Staff**

There are currently eight staff that deliver the weight management programme. There are currently six physiotherapists and two specialist nurses who deliver the

pulmonary rehabilitation programme. Four out of the eight weight management programme staff will receive the Verbal Health Literacy training. Six physiotherapists and two specialist nurses from the pulmonary rehabilitation programme will receive the training. All staff from the two participating services who receive the training, n=12, and from the wider services who complete the training during the study period, will be asked to complete the three questionnaires.

All trained staff, from each of the two services (n=12) where possible, will be observed pre and post the intervention and be part of the focus groups.

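### Collapsing the four-level observation rating to two levels for McNemar's test on at most 12 pairs discards some changes in frequency of use and leaves low power unless more than about half of staff cross the cut

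*Combined protocol and SAP*

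**What the plan says.** Section 3.4 sets out to find whether trained staff use the three techniques more or less often after training. A checklist records "how often each of the three communication techniques are used: never, sometimes, most of the time, all of the time". It covers "4 staff in the weight loss service and 8 staff in the pulmonary rehabilitation service", each assessed once before and once after training.

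Section 3.10.2 expects that "There will be 24 completed checklists for 12 members of staff observed before and after the training". One 2x2 table per technique then compares use "most/all of the time versus sometimes/never, pre training and post training", and "We will make this comparison using McNemar's Test".

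Twelve pairs is a ceiling. Section 3.4 says "If all agree the researcher will observe 24 sessions in total", and section 3.9.1 says "All trained staff, from each of the two services (n=12) where possible".

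The plan gives no reason for the cut-point and does not say which version of McNemar's test is meant. It states no significance level, expected effect or power for this analysis, and it plans no analysis of the four-level rating.

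**The concern.** The purpose in section 3.4 is change in frequency, and the scale has four steps of frequency. The analysis keeps one boundary, between sometimes and most of the time. For staff newly taught teach-back or chunk and check, going from never to sometimes is a plausible gain. In the 2x2 table that person is a concordant pair and adds nothing to McNemar's statistic. The same is true of a move from most to all of the time. The information is collected and then not used.

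These observations are the study's directly observed before/after evidence on objective (c), how the techniques are put into practice. The theory of change in section 1.3.7 runs through staff communication, and section 8 commits the team to explaining why if patient outcomes do not improve. A non-significant 2x2 result would inform that explanation poorly if several staff had in fact moved up a level.

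**Working it through.** **The plan's own count.** (4 + 8) staff x 2 sessions = 24 checklists, or 12 pairs. This agrees with section 3.10.2. There is no power figure to reproduce.

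**Assumptions.** Two-sided alpha of 0.05, borrowed from the weight calculation in section 3.9.3, and the exact (binomial) McNemar test. The plan states neither for this analysis.

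**What significance requires.** With b staff crossing up and c crossing down (b > c), p = 2 x P(X ≤ c), where X ~ Binomial(b + c, 0.5).

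| Up–down | Exact p |
|---|---|
| 5–0 | 2/32 = 0.063 |
| 6–0 | 2/64 = 0.031 |
| 7–1 | 2 x (1+8)/256 = 0.070 |
| 8–1 | 2 x (1+9)/512 = 0.039 |
| 10–2 | 2 x (1+12+66)/4096 = 0.039 |

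So at least 6 of 12 must cross with no reversals, at least 8 with one reversal, or 10 with two.

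**Power of the exact test, 12 pairs.** With no reversals, power is P(Binomial(12, π) ≥ 6), where π is the proportion of staff crossing upward. The last column allows 5% to cross downward, by summing the trinomial probabilities of all significant tables.

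| π | No reversals | 5% reversals |
|---|---|---|
| 30% | 12% | 8% |
| 40% | 34% | 23% |
| 50% | 61% | 42% |
| 60% | 84% | 61% |
| 70% | 96% | 77% |

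Power of 80% needs about 58% crossing upward with no reversals, or about 73% with 5% reversals. If only 8 staff take part and half cross, none reversing, exact power is 15%.

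**Other versions of the test (12 pairs, no reversals).** The mid-p version gives 28% at 30% crossing and 81% at 50%. The uncorrected asymptotic version gives 51% and 93%. The continuity-corrected version matches the exact test. All of them ignore moves within a collapsed category.

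**Two levels against four on the same 12 pairs.** The documents give no baseline or follow-up distribution, so these are assumed. Pairs were simulated from a latent normal model with within-person correlation 0.4, using exact tests at 0.05 two-sided. Distributions are percentages at never/sometimes/most/all.

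| Before → after | McNemar | Signed-rank | Sign test |
|---|---|---|---|
| 50/40/10/0 → 10/50/30/10 | 14% | 70% | 67% |
| 60/30/10/0 → 10/60/25/5 | 3% | 69% | 67% |
| 30/50/20/0 → 5/35/40/20 | 33% | 74% | 69% |
| 20/70/10/0 → 10/20/50/20 | 81% | 79% | 73% |
| 10/80/10/0 → 5/25/60/10 | 81% | 77% | 76% |

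Repeat runs differ by about 1 to 2 percentage points. In the first three rows 30 to 60% of staff start at never. In the last two, movement is mainly from sometimes to most. With no change, none of the tests rejected in more than 2% of data sets, so the ordinal tests do not gain power through excess false positives.

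**The case against.** The cut-point can be defended. It separates routine from occasional use and yields a percentage that the services can read easily. If training mainly moves people from sometimes to most of the time, McNemar's test does as well as the ordinal tests or slightly better, and the documents do not show which pattern to expect. The signed-rank test also has a cost: it treats never-to-sometimes as the same size of step as most-to-all. All of this stands. It is why the most/all percentage should stay as a summary, and why the gain cannot be given as one figure.

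A reader might go further in four ways that the documents do not support.

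- *The test has almost no power.* Power depends on how many staff cross, and no expected effect is stated. The exact test reaches 61% at half crossing and 84% at 60%, with no reversals.
- *Every crossing must go the same way.* It need not: 8–1 and 10–2 are both significant.
- *The p-value thresholds are fixed by the plan.* Section 3.10.2 does not name the exact version, and the mid-p and asymptotic versions are less demanding.
- *This is the only objective evidence on practice, and a null result will be taken as no change.* The 8-week questionnaire and the focus groups also address use in practice, though by self-report. The ratings are made by the lead researcher with no blinding described, so they are directly observed rather than clearly objective. Nothing in the plan says how a non-significant result will be read.

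**Conclusion.** The point holds in a limited form. Section 3.10.2 discards changes within the two collapsed categories, although detecting change in frequency is the stated purpose. Under the exact test at two-sided 0.05, power is low unless more than about half of staff cross the most/all boundary, and lower still with reversals or fewer than 12 staff. Using all four levels gains a great deal when many staff start at never (in the assumed scenarios, 69 to 74% for signed-rank against 3 to 33%). It loses little when movement is mainly across the cut (2 to 4 points for signed-rank, 5 to 8 for the sign test).

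The loss of information follows directly from sections 3.4 and 3.10.2. The power figures rest on the assumed alpha, test version, distributions and correlation. The observations belong to the process evaluation and are not a primary outcome, so the priority is modest.

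**What to change.** The number of pairs is capped by the number of trained staff, so the remedy lies in the analysis. In section 3.10.2:

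- For each technique, compare the paired four-level ratings with an exact sign test or an exact Wilcoxon signed-rank test. Name the chosen test and the significance level before the data are seen.
- Show the 4x4 before/after table, with the numbers of staff who improved, stayed the same and worsened.
- Keep the most/all percentage before and after as a descriptive summary. If McNemar's test is also kept, say which version.

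This takes a sentence or two and needs no new data or extra work from staff. The costs are a slightly less simple p-value, an equal-step assumption if signed-rank is used, and a small loss of power if nearly all movement crosses the most/all cut. The sign test avoids the equal-step assumption but has somewhat less power than signed-rank.

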#### 3.10.3 Quantitative staff data

The three staff questionnaires will be analysed separately because they each ask a different set of questions. Analysis will be descriptive e.g. showing the percentage staff finding the training helpful or not, and using it in practice or not. We will also test relationships between variables from different time periods. In particular we will give

each staff member a unique ID and compare their experiences after the training and two months later to see if staff who found the training helpful report that have been able to continue to use the techniques. We are undertaking this analysis on all staff receiving training from any service, not just the 12 staff from the weight management and pulmonary rehabilitation services.

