### **2.3. Objectives**

- a) To understand staff perceptions of the acceptability and feasibility of the Verbal Health Literacy training session, and the support to use the techniques in practice from the Health Literacy Officer.
- b) To understand staff knowledge of the Verbal Health Literacy techniques and their confidence and skills to use them.
- c) To understand how the Verbal Health Literacy techniques taught in the training session are being actioned in practice.
- d) To determine whether subjective Health Literacy and activation skills, such as the ability to self-manage, engage with healthcare services and understand what actions to take, are improved for service users after attending programmes delivered by Verbal Health Literacy trained members of staff.
- e) To measure the impact of the Verbal Health Literacy training on health and wellbeing outcomes.
- f) To describe the Index of Multiple Deprivation quintile of attendees at programmes and compare with the Derbyshire population in order to assess impact on health inequalities.

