#### **3.3 Staff perceptions of the acceptability and feasibility of the training and support, and their knowledge, confidence and skills to use the techniques taught**

##### **3.3.1 Pre and post intervention questionnaires**

The Health Literacy Officer collects pre and post training questionnaire data as part of their practice. This data will be made available to the research team with consent from individual staff undergoing the training. Questionnaire data will be collected,

with consent, from staff from the two participating services who receive the Verbal Health Literacy training. The Health Literacy Officer will also be training staff from other services in Derbyshire Community Health Services and the Local Authority during this time. She will be collecting the same questionnaire data from them.

Therefore, we will ask these additional staff (approximately 60), who receive the Verbal Health Literacy training during the period of the study, to consent to their questionnaire data to be used in the study also. Staff will be asked to complete a short questionnaire at three time points.

1. Baseline data will be collected from staff, via a short questionnaire, prior to their attendance at the training session. The data collected at this stage will include demographic data and ascertain their current knowledge of Verbal Health Literacy techniques and whether they have had Health Literacy training in the past
2. Staff will complete a short questionnaire immediately after they have attended the Verbal Health Literacy training. This will include questions about how useful they found the training and their confidence to use the techniques taught.
3. Staff will complete a final short questionnaire 8 weeks after attending the Verbal Health Literacy training to assess their perceptions of whether they are using the techniques they learnt in their routine care provision, the facilitators and barriers faced and any support they may require helping them use the techniques in their practice.

The questionnaires will be distributed online. This will be via the Derbyshire Community Health Services NHS Foundation Trust Microsoft forms web-based package. The forms will be distributed via the Health Literacy Officer's NHS Microsoft 360 office account. The Health Literacy Officer will share the anonymised, consented data with the lead researcher via email in a password protected spreadsheet.

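### Knowledge and confidence are not described as measured both before and after training, so the linked staff questionnaires cannot estimate within-person change in either.

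*Combined protocol and SAP*

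**What the plan says.** Objective (b) in section 2.3 is "To understand staff knowledge of the Verbal Health Literacy techniques and their confidence and skills to use them". The main quantitative source is a set of three online forms described in section 3.3.1:

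- **Baseline**, before the session: demographic data, and questions to "ascertain their current knowledge of Verbal Health Literacy techniques and whether they have had Health Literacy training in the past".
- **Immediately after training**: "This will include questions about how useful they found the training and their confidence to use the techniques taught".
- **8 weeks after training**: a form "to assess their perceptions of whether they are using the techniques they learnt in their routine care provision", together with facilitators, barriers and support needs.

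Section 3.10.3 then says: "The three staff questionnaires will be analysed separately because they each ask a different set of questions". The analysis is descriptive. Records carry a unique staff ID, and the one cross-time comparison named relates how helpful staff found the training to whether they report still using the techniques about two months later. It covers all trained staff from any service. Section 3.9.1 gives the core group as "All staff from the two participating services who receive the training, n=12", and section 3.3.1 adds approximately 60 staff from other services who will be asked to consent.

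**The concern.** Section 3.3.1 is headed as pre and post questionnaires, and records are to be linked by person. A reader would expect that to yield a before-and-after measure of what the training is meant to alter in staff. On the listed content it does not. Knowledge has a starting value and no later one. Confidence has a value straight after the session and no starting one, so high confidence after training cannot be told apart from confidence that was already high.

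This matters most if the result is null. Section 8 says that if patient outcomes do not change, dissemination will concentrate on why. Whether staff came away knowing more or feeling more confident is an obvious early question, and the largest staff data set could not answer it quantitatively.

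**Working it through.** **Step 1: which construct is listed on which form (section 3.3.1).**

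| Construct | Baseline | Immediately after | 8 weeks |
|---|---|---|---|
| Knowledge of the techniques | listed | not listed | not listed |
| Confidence to use them | not listed | listed | not listed |
| Perceived use in practice | not listed | not listed | listed |

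A within-person change score needs the same measure on at least two forms. Knowledge appears on 1 of 3 and confidence on 1 of 3. No pair can be formed for either, whatever the response. Section 3.10.3 agrees, since it gives differing questions as the reason for separate analysis.

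**Step 2: do other parts of the plan fill the gap?**

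- Sections 3.4 and 3.10.2 assess observed use of the three techniques before and 12-16 weeks after training in up to 12 staff, with McNemar's test for each technique. This is a real paired measure, but of behaviour.
- Section 3.10.3 links perceived helpfulness to later use. That is an association between two different variables, not change in one.
- Section 3.3.2 adds focus groups with the same 12 staff. They give qualitative insight and no estimate of change.

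**Step 3: numbers available.** The plan's core figure reproduces: 4 weight management staff + 6 physiotherapists + 2 specialist nurses = 12. Adding the approximately 60 others gives 12 + 60 = about 72 invited. The plan gives no sample size, power or response rate for the questionnaires, so there is no further figure to reproduce.

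**Step 4: what repeated items would give.** The 95% half-width for a mean paired change, in SDs of the change score, is t(0.975, n-1) / sqrt(n).

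- n = 72 (every invited person completes both forms): 1.994 / 8.485 = 0.235
- n = 36 (50% return, assumed): 2.030 / 6 = 0.338

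The detectable mean change at 80% power and two-sided 5% (both assumed), by normal approximation, is (1.960 + 0.842) / sqrt(n).

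- n = 72: 2.802 / 8.485 = 0.33 SD
- n = 36: 2.802 / 6 = 0.47 SD
- n = 12 (core staff only): 2.802 / 3.464 = 0.81 SD

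The wider group therefore makes the paired estimate usefully precise. The 12 core staff alone would not.

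**The case against.** The strongest reply is that the plan never promises a change estimate here. Objective (b) is about understanding. Where change is wanted the plan says so: objective (d) speaks of improvement, objective (e) of impact, and section 3.4 is titled as an assessment of change. The questionnaires serve a process evaluation and their analysis is declared descriptive. This stands: the point is a limit on inference and not an internal contradiction.

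Several stronger readings are tempting and are not supported:

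- A reader might infer that the three forms have no items in common. The forms are not reproduced, and the wording for the first two is not exhaustive, so incidental overlap cannot be ruled out. What can be said is that no knowledge or confidence item is described on both sides of the training.
- A reader might infer that the staff data cannot show any effect at all. The first step in the theory of change (section 1.3.7) is that staff communicate more simply and check understanding. That behaviour is observed before and after training.
- A reader might infer that the ID linkage is pointless without repeated items. It has a stated use, relating helpfulness to later use.
- A reader might take 72 as the number of linked records. It is the number invited; consent and non-response will lower it.

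It is also fair to say that the fix has limits. Only trained staff complete the forms, so a paired change would be self-reported and uncontrolled, and would not prove that the training caused it. Baseline confidence in a technique may mean little to someone who has never met it.

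**Conclusion.** The point holds in a narrow form. As sections 3.3.1 and 3.10.3 describe the forms, within-person change in knowledge and in confidence cannot be estimated at any sample size, and neither the observations nor the focus groups supply it. With repeated items the same staff would give a 95% half-width between about 0.235 SD (72 complete pairs) and 0.34 SD (36 complete pairs) of the change score. This rests on the listed content reflecting the actual forms, on roughly 60 additional staff being trained, and on an assumed return of 50% to 100%. It is a low-severity point: a worthwhile and cheap improvement. It does not touch the service-user outcomes.

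**What to change.** 1. Before baseline forms go out (section 6 places training and the first two forms in July-August 2024), add one identical knowledge item and one identical confidence item for each of the three techniques, six items in all, to all three forms.
2. Carry the planned unique ID on the baseline form as well as the two later ones.
3. Add to section 3.10.3 that paired change from baseline to post-training, and from baseline to 8 weeks, will be reported with 95% confidence intervals and the number of complete pairs, and described as uncontrolled self-reported change. Allow a response for staff unfamiliar with a technique at baseline, and report how many choose it.
4. If the items cannot be added in time, state in section 3.10.3 that change in knowledge and confidence will not be estimated. A missed baseline cannot be recovered.

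The cost is six short items on online forms already run by the Health Literacy Officer, plus a short addition to the analysis section. The downsides are slightly longer forms in a tool that also serves staff outside the two study services, and baseline confidence scores that need care in interpretation.
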